Our hypotheses were formulated in line with PICOS (Population-Intervention-Comparison-Outcome-Study); significance was set at 0.05 (Higgins et al., 2019). In addition to standard applications, the intervention group will be using the PREDIABE-T^R mobile app. The control group will only use standard applications. In this context, our research hypotheses are the following:

H1a: When compared with the control group, the eating behaviors with regard to adopting the Mediterranean Diet of prediabetic adults using the PREDIABE-T^R app will be at a higher level.

H1b: When compared with the control group, the physical activity (MET, number of steps) of prediabetic adults using the PREDIABE-T^R app will be at a higher level.

H1c: When compared with the control group, the metabolic parameters (A1C, Impaired Fasting Glucose-IFG, Impaired Glucose Tolerance-IGT) of prediabetic adults using the PREDIABE-T^R app will be at lower levels.

H1d: When compared with the control group, prediabetic adults using the PREDIABE-T^R app will lose more weight.

METHODS

Study design

This study protocol was drawn up for a single center, single-blind (participant), pretest-posttest, follow-up, parallel group (1:1 ratio) randomized controlled trial (Fig.1). The study protocol was prepared on the basis of the following Standard Protocol Items: Recommendations for Interventional Trials (SPIRIT) guidelines (Chan et al., 2013) and the Consolidated Standards of Reporting Trials, Non-Pharmacological Treatment Interventions Checklist (CONSORT-NPT) (Boutron et al., 2017). The study was registered on ClinicalTrials.gov on XXX with the ID XXXX.

Study setting and population

This study will be carried out at the Yıldırım Beyazıt Family Health Center (FHC) No. 9, a facility in the city of Kutahya, in western Türkiye. No. 9 is an FHC that addresses a large city population and where 5 physicians and 5 midwives work. The target sample will consist of prediabetic adults. The study will be conducted in the FHC between January and July 2023.

Sample size determination

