The study universe will consist of adults of the ages 45-65 who have received a diagnosis of prediabetes and are registered at the Kütahya FHC No. 9. The sample size determined by power analysis is based on calculations made with the G-Power program that were used in a similar study. Effect size is 0.666 (Chen et al., 2015, Everett et al., 2018); level of significance, 0.05; confidence interval limit 95%; testing power, 90%. The optimal number of participants calculated in the two-way hypothesis review was found to be 49 for each group. In previous studies (Chen et al., 2015; Zhang et al., 2017), the size was increased by 10% to allow for losses. Ultimately, the decision was to enroll 60 participants in each group.

Inclusion criteria

- Individuals to be included will be those who: are prediabetic (Impaired Fasting Glucose-IFG=100-125 mg/dl-mmol/L, A1C=5.7%-6.4% or Impaired Glucose Tolerance-IGT=140-190 mg/dl-mmol/L),
- are active Android/IOS cell phone users,
- are not pregnant or have any malignancy,
- have no hearing or vision impairment,
- are at least primary school graduates and fluent in Turkish.

Exclusion criteria

- Individuals who have a diagnosis of diabetes or are using an insulin pump or oral antidiabetic agents,
- have vision impairment,

[figure not shown]
- are pregnant,
- have any condition that precludes engaging in physical activity,
- have psychiatric issues or problems with communicating, will be excluded.

Randomization

The stratified block randomization (1:1) will be used to attain objectivity in assigning individuals to the experimental group that will be using the mobile app and to the controls who will be following routine practices (Brugnara et al., 2016; Kautzky-Willer et al., 2016; Kautzky-Willer et al., 2019). The variable “**gender**” will be used as the control variable in the stratified block randomization.

Blinding and Preventing Bias

The researchers cannot be blinded in this study since they were the parties to develop the application and will be involved in the training. On the other hand, the participants can be blinded because they are to be using either the PREDIABE-T^R app or the Türkiye Nutrition Guide. In order to prevent bias, the collection of the randomized assignment data will be handled by a researcher who is not actively involved in the study; this researcher will submit the data in opaque envelopes to the implementing researcher.

Intervention Group

PREDIABE-T^R mobile app group

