Prediabetic individuals 45 years of age and over will be asked to use the PREDIABE-T^R mobile app. The researcher will demonstrate how the application can be downloaded to the participants' phones and how to use it. Before the PREDIABE-T^R app is sent out to the participants, its content will be reviewed for suitability and content validity by health professionals and experts in health communications, informatics, and social media. The mobile app will be used and the process monitored for a period of 6 months. Each week, healthy eating and physical activity messages will be sent over the mobile app and a daily step count will be announced. Education about prediabetes, the risk of diabetes, the calculation of the body mass index, as well as other motivating self-evaluation tools and notifications will be sent out via the PREDIAB-T^R mobile app. The adherence of the experimental group to the intervention will be assessed in the software and encouraging messages will be sent out to ensure continued use of the app. For example: Bracelets inscribed with "Congrats! You've reached your daily steps goal!" or "Keep Active, Keep Protected from Diabetes!" will be distributed as gifts. If requested, the researcher will come to the FHC one day every week to meet with the participants.

The application consists of a total of 3 parts and 4 modules (Figure 2).

- **Module 1: Personal data**

Containing data on the participant's age, gender, telephone number, email and perception of his/her health (bad, so-so, good, very good).

- **Module 2: Medical history of the participant**

In this module, the participants tick the items that apply to themselves or their first-degree relatives by marking the conditions in their medical history that may increase the risk of prediabetes. Additionally, in line with the recommendations of the Turkish Association of Endocrinology and Metabolism, this module contains the Finnish Diabetes Type-2 Risk Score (FINDRISK) which assesses an individual's risk of diabetes (TEMD, 2020).

- **Module 3: Healthy lifestyle behaviors**

The sub-sections of the module are devoted to nutrition, height-weight-body mass index (BMI) and physical activity.

Nutrition

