Ethical Considerations in the Study

Ethical approval for the conduct of the study was obtained from Akdeniz University Faculty of Medicine Clinical Studies Ethics Committee (Date: 16.03.2022, No. KAEK-192) and institutional approval from the Kütahya Provincial Health Directorate (Date: 30.05.2022, No. 2022/47). Additionally, the written informed consent of the individuals to be included in the study will be collected. The study was conducted in compliance with the ethical principles of the Declaration of Helsinki. It was registered on ClinicalTrials.gov on **XXXXX**.

Validity-Reliability

The study protocol was drawn up based on the SPIRIT (Chan et al., 2013) and CONSORT-NPT (Boutron et al., 2017) guidelines. Randomization and blinding will reduce bias in the results. The measuring instruments used in this study are valid and reliable (Block et al., 2015; Etbaş Demirağ, 2016; Güler, 2019; McLeod et al., 2020; Özkan Pehlivanoğlu et al., 2020; Sağlam et al., 2010; Toro-Ramos et al., 2020).

Data Analysis

The data will be analyzed with the SPSS (Statistical Package for the Social Sciences) 23.0 package program licensed by Akdeniz University Faculty of Medicine Department of Biostatistics. The G*Power 3.1 program was used in determining sample size. Intention to Treat (ITT) analysis will be employed for the analysis of lost data. Descriptive statistics will be defined by means and standard deviation. Numbers, percentage distribution, the chi-square and t test will be used to identify homogeneous groups. To test normality, skewness and kurtosis values will be taken as a basis for the Shapiro-Wilk test. The one-way ANOVA, two-way ANOVA and ANCOVA tests will be used for dependent and independent groups. Non-parametric equivalents of correlation and regression analyses will be considered in the non-parametric analysis.

DISCUSSION

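### The plan labels the trial participant-blind and relies on blinding to reduce bias, but describes no masking, so the questionnaire primary outcomes are open to differential reporting

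*Combined protocol and SAP*

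**What the plan says.** Under Study design, the trial is a "single center, single-blind (participant), pretest-posttest, follow-up, parallel group (1:1 ratio) randomized controlled trial".

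Under Blinding and Preventing Bias, the plan states: "The researchers cannot be blinded in this study since they were the parties to develop the application and will be involved in the training". For participants it says the opposite: "the participants can be blinded because they are to be using either the PREDIABE-T^R app or the Türkiye Nutrition Guide". It then describes a researcher outside the study who handles the random assignment: "this researcher will submit the data in opaque envelopes to the implementing researcher".

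Under Validity-Reliability, the plan concludes: "Randomization and blinding will reduce bias in the results".

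The arms are described in three ways:

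- Blinding and Preventing Bias has participants using one app or the other.
- Hypotheses says: "In addition to standard applications, the intervention group will be using the PREDIABE-T^R mobile app". The controls have the standard applications only.
- Randomization describes the controls as receiving routine practice.

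For the app arm, the Intervention Group section says: "The researcher will demonstrate how the application can be downloaded". The Active Control Group section likewise has controls taught to download and use the Ministry's nutrition app.

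Under Outcome criteria, the primary outcome covers Mediterranean diet adherence, physical activity and metabolic values. The instruments for the first two are MEDAS (14 questions) and the IPAQ Short Form (7 questions). Data Collection says the form is completed by self-report.

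**The concern.** The reason given for participant blinding is that the two arms use different products. That difference is what lets a participant see which arm they are in. If the label stands, a reader will credit the trial with a protection that no described procedure provides.

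The consequence falls mainly on MEDAS and IPAQ. Participants who know which programme they follow may answer diet and activity questions differently for that reason alone. The app also teaches its users 14 recommendations taken from MEDAS, so one arm is coached on the content of an outcome scale. A difference in H1a, or in the IPAQ part of H1b, could then mix real behaviour change with a change in reporting. The planned analysis cannot separate the two.

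**Working it through.** **1. Is any masking procedure described?** The relevant sections, side by side:

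| Element | What the plan describes | Does it mask the app received? |
|---|---|---|
| Participants | Two different, named apps | No |
| Researchers | Stated to be unblinded | No |
| Opaque envelopes | Conceal the upcoming assignment | No; this is allocation concealment |
| Sham or look-alike app | Not described | – |
| Hypothesis withheld from participants | Not described | – |
| Check on the success of blinding | Not described | – |
| Blinded assessor or analyst | Not described | – |

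**2. Do the arms look different to participants?** Weekly messages, an announced daily step count, gold stars, inscribed bracelets and direct messaging to the researcher are described only for PREDIABE-TR. So are the 14 MEDAS recommendations (Intervention Group, Nutrition, Physical Activity and Communications). App instruction is described for both arms and does not separate them.

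**3. Does the stated reason fit the rest of the plan?** An either/or contrast does not fit the add-on contrast under Hypotheses or the routine-practice control under Randomization.

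**4. Reproducing the plan's sample size.** Inputs from Sample size determination: effect size 0.666, significance level 0.05 (two-sided), power 90%. A two-sample t-test using the noncentral t distribution needs 48.36 per group, rounded up to the stated 49. Power at 49 is 0.904. The plan's figure reproduces, and this point does not dispute it.

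**5. What a reporting shift could do (illustration).** Suppose the true effect is zero and knowledge of the arm shifts self-report by b SD in one arm. With n per group:

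- Noncentrality: δ = b × √(n/2)
- Degrees of freedom: 2n − 2
- Chance of a significant result: P(|T| > t₀.₉₇₅), where T is noncentral t with parameter δ

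For n = 49, √(49/2) = 4.950, df = 96 and the critical value is 1.985. For n = 60, √(60/2) = 5.477, df = 118 and the critical value is 1.980.

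| Assumed shift b (SD) | δ, n = 49 | Significant, n = 49 | δ, n = 60 | Significant, n = 60 |
|---|---|---|---|---|
| 0.1 | 0.495 | 7.8% | 0.548 | 8.4% |
| 0.2 | 0.990 | 16.5% | 1.095 | 19.2% |
| 0.3 | 1.485 | 31.2% | 1.643 | 37.1% |
| 0.4 | 1.980 | 50.0% | 2.191 | 58.4% |
| 0.5 | 2.475 | 68.8% | 2.739 | 77.5% |

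The nominal rate is 5%. The values of b are assumptions; the documents give none. At a fixed shift, the larger sample makes the false-positive rate higher.

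**The case against.** Several arguments on the other side have weight.

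- **Partial masking is possible.** With an active control, participants could be kept unaware of the hypothesis or of which app is under test. The consent pages are not in the supplied text, so what participants are told cannot be checked. A reader might infer that participants know they have the developers' own app, but no section says they are told who built it. This stands, and the fix allows for it. It does not rescue the label: the plan does not offer this as its reason, and withholding a hypothesis does not hide which app a person uses.
- **Instruction is matched in part.** Both arms are taught to use an app. A reader might also infer that the researcher installs PREDIABE-TR, but the text speaks only of demonstrating the download. Both limits stand.
- **The plan's claim is modest.** A reader might infer that the outcomes are presented as fully protected from bias. The text says only that bias will be reduced. Even that modest claim needs a procedure behind it.
- **H1b is not only questionnaire data.** It also names step counts. The concern covers the IPAQ part; how steps are captured in controls is not described.
- **The percentages depend on the assumed shift.** This is correct. At 0.1 SD the rate stays fairly near nominal, and 0.5 SD is 75% of the planned effect (0.5/0.666). Relabelling the trial does not change any bias. It changes what readers are told and what may be concluded.
- **The Conclusion already ties effectiveness to metabolic parameters such as A1C.** This partly answers the worry about claims resting on questionnaires alone, but the plan states no such limit for MEDAS or IPAQ.

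**Conclusion.** The point holds as a matter of labelling and interpretation. The plan describes no procedure that masks participants to the app they use, and it states that the researchers are unblinded. The single-blind label and the appeal to blinding under Validity-Reliability are therefore unsupported. MEDAS and the IPAQ part of H1b are exposed to differential reporting.

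The size is unknown. The figures of 7.8% to 68.8% (49 per group) and 8.4% to 77.5% (60 per group) hold only under an assumed shift of 0.1 to 0.5 SD, no true effect and a simple two-sample t-test. They show sensitivity and are not a forecast for this trial.

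A reader might go further and conclude that the effectiveness claim should rest on A1C alone. The documents do not support that step. Outcome criteria names diet, activity and metabolic values together as primary, and the A1C section takes results from any health facility during the study with no fixed time point. Nor are the metabolic measures wholly free of the problem: an unblinded researcher takes the glucose readings. They do avoid self-report.

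**What to change.** 1. **Study design:** replace the single-blind (participant) label with open-label.
2. **Blinding and Preventing Bias:** replace the sentence that participants can be blinded with a statement that they know which app they use. If anything is withheld, such as the hypothesis, say exactly what. Keep the envelopes, described as allocation concealment.
3. **Validity-Reliability:** delete the reference to blinding, leaving randomization.
4. **Arm descriptions:** reconcile the either/or, add-on and routine-practice accounts.
5. **Data Analysis:** code the arms A and B for the person running the analysis until it is final. This protects analytic choices; it does not remove self-report bias.
6. **Interpretation:** state that MEDAS and IPAQ differences are unblinded self-report. They will not on their own support a claim of effectiveness without support from the non-self-reported metabolic measures. This agrees with the Conclusion and leaves the primary outcome structure unchanged.

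The cost is wording and a coded data file, with no change to sample size. The downside is a less favourable design label and a more cautious conclusion for H1a and the IPAQ part of H1b.

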Data will be collected on the individuals' sociodemographic features, gender, age, education, profession and medications they are taking. Their diabetes risk will be measured by means of the Finnish Diabetes Type-2 Risk Score (FINDRISK). The data collection form will be filled out on the basis of self-reporting. FINDRISK was developed in 1987 by Tuomilehto and Lindström to identify individuals at risk of Type-2 diabetes mellitus without laboratory testing (Lindström et al., 2003). The Turkish validity and reliability study for FINDRISK was performed by Etbaş Demirağ in 2016 (Etbaş Demirağ, 2016). The participants' metabolic measurements will be taken by a researcher using the

Accu-Chek® Performa Nano device from a capillary blood sample; A1C values will be retrieved from FHC records.

Outcome criteria

The expected primary outcome is a change in the adherence to the Mediterranean diet, physical activity levels and in the prediabetes metabolic values of the adults. The secondary outcome is a change in the adults' ability to achieve weight loss.

Primary outcome criterion

Mediterranean Diet Adherence Screener-MEDAS)

The Turkish validity and reliability studies for MEDAS, which was originally developed in 2012 by Martínez-González et al., were performed by Özkan Pehlivanoglu et al. in 2020 (Martínez-González et al., 2008; Özkan Pehlivanoglu et al., 2020). MEDAS consists of 14 questions (León-Muñoz et al., 2012). Each question is worth 1 or 0 points, depending on consumption. A total score of 7 or above indicates that the individual is adhering to the Mediterranean diet at an acceptable rate; a score of 9 or above indicates strict adherence. Cronbach's alpha coefficient for the scale is reported to be 0.829.

International Physical Activity Questionnaire (IPAQ)

The IPAQ International Physical Activity Questionnaire-Short Form was developed in 1996 by Booth in order to identify the risk factors of inactivity and physical activity levels in prediabetes. The Turkish version of the IPAQ-Short Form consisting of 7 questions will be used. The Turkish validity and reliability studies for this questionnaire were conducted by Saglam et al. (Öztürk, 2005; Saglam et al., 2010).

Metabolic Measurements

The participants' A1C, fasting blood glucose-postprandial blood glucose (whichever is appropriate for the individual) values will be measured.

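### Four primary measures are unranked under a single 0.05 level with no testing rule, while the sample size covers one comparison on an unnamed endpoint

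*Combined protocol and SAP*

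**What the plan says.** Outcome criteria defines the primary outcome across three domains: "The expected primary outcome is a change in the adherence to the Mediterranean diet, physical activity levels and in the prediabetes metabolic values". Weight loss is the only outcome made secondary there. Under Primary outcome criterion the plan then describes MEDAS, IPAQ and the metabolic measurements. The last are A1C and "fasting blood glucose-postprandial blood glucose (whichever is appropriate for the individual) values will be measured". That makes four measures, and none is placed above another.

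Hypotheses gives one level for everything: "significance was set at 0.05". It sets out H1a to H1d by domain. H1b covers more than one measure ("the physical activity (MET, number of steps) of prediabetic adults"), and so does the metabolic hypothesis ("H1c: When compared with the control group, the metabolic parameters (A1C, Impaired Fasting Glucose-IFG, Impaired Glucose Tolerance-IGT").

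Sample size determination uses an effect size of 0.666, a level of 0.05 and 90% power. It reports: "The optimal number of participants calculated in the two-way hypothesis review was found to be 49 for each group". It adds "the size was increased by 10% to allow for losses" and settles on 60 per group. The effect size is attributed to two cited studies but not to any of this trial's outcomes.

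Data Analysis names tests in general terms: "The one-way ANOVA, two-way ANOVA and ANCOVA tests will be used for dependent and independent groups". It assigns no test to an outcome and says nothing about order, adjustment, or how many of the primary measures must succeed. The Conclusion has one informal sentence that would call the app effective if metabolic parameters fall; A1C is its example, and no comparator is named.

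**The concern.** With four primary measures and no rule joining them, the plan does not say what result would count as a positive trial. Nothing in it prevents the most favourable of the four from being reported as the primary finding. If that is allowed, the error rate for the primary outcome as a whole exceeds 0.05. If all four are meant to succeed, the error rate is protected, but the stated 90% is the power of one test and not of the whole requirement. The Abstract and Conclusion say the findings are meant for policy-makers, so the claim the trial can support should be fixed before any outcome is known.

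**Working it through.** **Inputs from the plan.** d = 0.666; two-sided level 0.05; 90% power; 1:1 allocation; 49 per group calculated, 60 enrolled; 10% loss (Study design, Hypotheses and Sample size determination). Analysed numbers considered: 49, 54 (60 × 0.9) and 60. Number of primary measures: k = 4 (Primary outcome criterion).

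**Assumptions, not in the plan.** d = 0.666 applies to every measure, and the four test statistics share a common correlation, shown from 0 to 0.8.

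**1. The plan's own figure.** Two-sample t-test, noncentrality d√(n/2), 2n − 2 degrees of freedom. For n = 49: 0.666 × √24.5 = 3.297, critical value 1.985, power 90.4%. For n = 48, power is 89.8%. So 49 reproduces, as one two-sided comparison at an undivided 0.05.

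**2. If any one success suffices.** For independent tests the chance of at least one false positive is 1 − (1 − 0.05)^4 = 1 − 0.8145 = 18.5%. Counting only false positives in the app's favour, it is 1 − (1 − 0.025)^4 = 9.6%. For correlated tests, equally correlated normal statistics with critical value 1.96 were integrated numerically:

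| Assumed correlation | Either direction | In the app's favour |
|---|---|---|
| 0 | 18.5% | 9.6% |
| 0.3 | 17.4% | 8.7% |
| 0.5 | 15.6% | 7.8% |
| 0.8 | 11.4% | 5.7% |
| One test, for reference | 5% | 2.5% |

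**3. If all four must succeed.** No inflation arises. Single-test power at 0.05 is 0.904, 0.929 and 0.951 with 49, 54 and 60 per group. If independent, joint power is the fourth power of each: 0.904^4 = 67%, 0.929^4 = 75%, 0.951^4 = 82%. At correlation 0.8, simulation gives about 81%, 85% and 89%.

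These are for an unadjusted t-test. With ANCOVA on baseline, and 0.666 taken on the unadjusted outcome SD, the effect becomes d/√(1 − r²), where r is the baseline–outcome correlation. With independent outcomes, joint power with 49, 54 and 60 per group is:
- r = 0.3: 74%, 81% and 87%
- r = 0.5: 87%, 91% and 95%

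The documents give no value for r.

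**4. If each hypothesis is claimed separately.** Then 0.05 and 90% describe each single test, provided 0.666 applies to it. They say nothing about the primary outcome as a set.

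**5. Holm over four measures.** The first step is at 0.05/4 = 0.0125. Unadjusted t-test power at that level is 77%, 82% and 86% with 49, 54 and 60 analysed per group. Reaching 90% needs 66 analysed per group (65 gives 89.5%).

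**The case against.** The strongest reply is that H1a to H1d are separate hypotheses, each entitled to its own 0.05, and that familywise control across them is a matter of policy. That reading is available. A reader might infer that 0.05 and 90% cannot both be right on any reading of the primary outcome. The documents do not support this: with separate claims both figures can describe each test, and with an all-must-succeed rule ANCOVA could bring joint power to 90% or more at the planned enrolment. What remains is that the plan states none of these readings, that Outcome criteria folds H1a to H1c into a single primary outcome, and that H1b and H1c each contain several measures.

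It is also tempting to count step count as a fifth primary measure. H1b mentions it, but Primary outcome criterion does not list it, and the plan describes step counting only within the intervention app. The count stays at four.

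The Conclusion's effectiveness sentence might be taken as the missing success rule. It covers only metabolic parameters, as an open list with no threshold or comparator, so it cannot serve. Read literally, with A1C and glucose as two independent tests, it would still give 1 − 0.95² = 9.75%.

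Finally, enrolling 60 gives some slack. At 0.0125 with no losses, that yields 86% on an unadjusted t-test, short of 90%.

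**Conclusion.** The concern holds and should be fixed. The primary outcome consists of four unranked measures with one 0.05 level and no rule for combining them, and the sample size supports one comparison on an unnamed endpoint. The arithmetic behind 49 is correct; what is missing is the link from that calculation to the primary outcome.

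The size depends on the rule intended. The error rate of 18.5% to 11.4% (9.6% to 5.7% in the app's favour) applies only if any one success may be claimed, which is inferred from the plan's silence and is not stated by it. The 67% to 82% joint power applies only if all four must succeed, are independent, each have d = 0.666, and are analysed by unadjusted t-test.

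A reader might also treat the 77%, 82% and 86% at 0.0125 as guaranteed minimum power. They are not. They fail if 0.666 does not apply to the measure, if A1C results are missing, or if glucose is divided between fasting and postprandial values so that fewer participants contribute to each. The between-measure and baseline correlations are all assumptions.

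**What to change.** Before outcome data are seen, choose one option and write it into Outcome criteria, Sample size determination and Data Analysis.

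(a) Name one primary endpoint, chosen by the sponsor, and make the rest secondary. Alternatively, test the listed primaries in a fixed order, each at 0.05, stopping at the first non-significant result. In both cases 49 per group stands for the first test, if 0.666 is justified for that endpoint.

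(b) Keep the four primaries, list them exactly, apply Holm, and restate first-step (0.0125) power as 77%, 82% and 86% with 49, 54 and 60 analysed per group. State that these figures are conditional on d = 0.666 for that measure, complete data at those numbers and an unadjusted t-test, and do not call them floors.

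If separate claims for each hypothesis are intended, say so, and say that 0.05 and 90% describe each single test only.

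In addition, reword the Conclusion's effectiveness sentence to match H1c, as a comparison between groups.

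**Cost.** This is wording only if the confirmatory measure is MEDAS or IPAQ. Any option using A1C depends on baseline and six-month results being available; the A1C Measurement text takes results from health-facility records and does not ensure one at six months. Any option using glucose must first settle which value is analysed for each participant. The downside is that fewer outcomes can support a confirmatory claim, or the stated power is lower; restoring 90% at 0.0125 on an unadjusted t-test would need 66 analysed per group.
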